Persistent and long-lasting health problems are common in patients after COVID-19 infection. In a recent study of patients that had been hospitalized with COVID-19, two months after discharge, 87% reported at least one lingering symptom (joint pain, fatigue, breathing issues, etc), more than 50% reported more than three lingering issues, and over 40% reported a reduction in their of quality of life. Another study found that at 1-month after hospitalization for COVID-19, 74% reported persistent issues related to shortness of breath and a decrease in both physical and mental health. Preliminary data from our Post-COVID Recovery clinic agree with these two recent reports. In our study, 1 1/2 months after COVID-19 diagnosis, patients reported on average 10 of the 18 common symptoms (with 90% having chest pain, 87% dyspnea, 75% fatigue, and 90% with cognitive changes). While the previous studies examined patients that had severe COVID-19 infections, >50% of our patients were never hospitalized, yet have numerous persistent symptoms. This has serious implications for the ability of patients to return to work, downstream effects on mental health due to sometimes drastic lifestyle and work capacity changes, and the ability to engage in activities or hobbies enjoyed prior to COVID-19 illness. In a current study we aimed to characterize the baseline endocrine, metabolic, inflammatory and microbiome alterations in the post-COVID syndrome patients to better identify and manage the symptoms to

prevent potential long-term health consequences. Two post-COVID subjects have been studied and both subjects had low levels of growth hormone secretion, consistent with BIAFAC subjects. Fecal microbiome analysis of the subjects using the BIAFAC 96 well qPCR array showed striking similarity to BIAFAC subjects showing low abundance of *Prevotella spp* and an absence of *P. copri*.

Therapeutic Rationale

As described above, our research team has developed a novel therapeutic strategy using rhGH that we have shown to be efficacious at improving fatigue, skeletal muscle function, cognitive function, and now appears to be positively impacting the connection between different brain regions as measured with fMRI.

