Given the data acquired from two PASC subjects under IRB 20-0361 that have shown indistinguishable profiles to those of BIAFAC communities as well as remarkably reduced GH responses to GST, we expect that the Power calculations explained in this section (above) will also apply to PASC. Because PASC is a recent consequence to the pandemic no data exist to complete Power calculations beyond those of syndromes like BIAFAC that present with similar symptoms. We therefore have proposed enrollment of at least 25 PASC subjects to compare to 25 normal controls already included in this protocol.

For quantifiable (primary) outcomes such as abundances of individual species in the GI microbiome and (secondary) symptom related outcomes, a standard repeated measure ANOVA model will be used. When possible, age and other covariates will be brought into the model to reduce variability and account for random differences between the two groups. Significance tests will be performed at the $\alpha=0.05$ level, and multiple testing corrections will be used to account for potential Type I error rate inflation. Nonparametric, generalized linear, and transformed response models will be considered as necessary to alter the model to account for deviations from standard assumptions (normality, linearity, etc.). Current data support statistical outcomes being established with group sizes similar or slightly larger size than our previous study.

The graph below is based on group difference in *Alistipes onderdonkii*. Power calculations were performed using t-tests with G*Power (two-groups, two-sided, $\alpha=0.05$, Version 3.1.9.2, Germany). Effect size in this case was 1.184.

Below is a list of organisms we identified previously and which were used to conduct the power analyses for the present study. Please note that the intestinal flora includes an incredibly diverse system of organisms and at this time it is difficult to accurately predict which organisms will be included in the biome shifts we expect to see. Therefore, additional organisms may be included in the final microbiome comparisons between mTBI patients and household control subjects. Further power analyses will be conducted using the data collected during this investigation.

Target	n = 20 (10/group)	n=30	n=40	n= 50 (25/group)
Alistipes onderdonkii	70.7%	87.9%	95.4%	98.4%
Desulfovibrio	60.4%	79.3%	89.9%	95.4%
Prevotella spp	97.5%	99.8%	100.0%	100.0%
Akkermansia	64.8%	83.2%	92.6%	96.9%

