- c. Potential subjects will be informed of all procedures involved in the study. If screening reveals any clinical abnormalities, subjects will be advised, by either a study team physician or nurse practitioner, to consult his/her primary physician. If the subject agrees to participate, written consent will be obtained in the presence of one of the following: the Principal Investigator, Co-Investigator, or Study Coordinator. There will always be at least one qualified member of the research team or one CRC nurse with the subject during the study protocol.

Plan for Data Management:

- a. All the study data will be collected by the research team and recorded on case report forms. To preserve confidentiality, immediately after enrollment each subject will be assigned a code by which each research sample will be identified for further analysis to avoid identification by non-qualified individuals. [name], the Principal Investigator, is the individual responsible for storage of data. Recognizable personal subject information will be stored in [name] laboratory in a locked cabinet.
- b. Data will be reviewed on a weekly basis by the PIs and the research team.
- c. The conditions that would necessitate early termination of the study include non-compliance with study medication dosing.
- d. The PI with the aid of the Co-Investigators and the Study Coordinator will perform aggregate analysis of data and adverse events.

Persons Responsible for Data Monitoring:

The ultimate responsibility for data and safety monitoring, and submitting reports of unanticipated problems, adverse events, protocol deviations and protocol violations rests with the Principal Investigator, [name]. Every effort will be undertaken to monitor and minimize the risks

to subjects. Prior to obtaining informed consent, subjects will be encouraged to thoroughly read the informed consent form and ask questions regarding the outlined procedures and risks. To ensure ongoing protection of study subjects all procedures will be performed under the supervision of [name]., or a physician willing to provide backup medical coverage. All study physicians will be familiar with the study protocol.

Reporting Unanticipated Problems, Adverse Events, Protocol Deviations and Protocol Violations:

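### The primary organism family is left open and the correction has no stated denominator, so the 0.05 error rate is not secured if organisms are added after group differences are seen

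*Combined protocol and SAP*

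**What the plan says.** Statistical Considerations (text under Aim 2) treats abundances of individual gut species as primary outcomes, introduced as examples and not as a closed list. On testing it says "Significance tests will be performed at the $\alpha=0.05$ level" and that "multiple testing corrections will be used to account for potential Type I error rate inflation". No method, error rate or family is named.

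The section then tabulates eleven targets, ten taxa plus 16S, and describes them as the organisms behind the power analyses. It does not call them the primary family. Its reason for going further is that "at this time it is difficult to accurately predict which organisms will be included in the biome shifts we expect to see". The next sentence draws the consequence: "Therefore, additional organisms may be included in the final microbiome comparisons between mTBI patients and household control subjects". No selection rule, cap, lock date or exploratory label is attached.

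Specific Aims 1a, 1b and 2 do not close the set either; their outcomes are genus, species and unnamed selected qPCR markers. The GI microbiome procedures plan next-generation sequencing as well as qPCR, so more than eleven targets are likely to be measured. The number is not given.

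**The concern.** The reason given for leaving the list open is that the shifting organisms cannot be foreseen. That makes an observed shift a natural route into the final comparison, although the text does not say it is the route. No blinding of those who analyse the data is described.

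A correction protects only the tests it counts. If many organisms are examined, those with the largest group differences are added, and the adjustment covers only the reported set, then the organisms examined and left out are not counted. The reported additions may then be the largest chance differences in the pool. On a primary outcome, a reader could not tell a prespecified altered organism from a chance one picked because it was extreme.

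**Working it through.** **Inputs from the plan.** Two-sided alpha 0.05; 25 per group; eleven listed targets; effect size 1.184 for *Alistipes onderdonkii* ("Effect size in this case was 1.184"); power method: "Power calculations were performed using t-tests with G*Power (two-groups, two-sided", alpha 0.05, with no adjustment shown.

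**Assumed inputs.** The number of targets assayed, M (30, 96 or 200), and the number of most-shifted organisms added, k (5, 10 or 20). Neither is in the documents.

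**The plan's own figure.** A two-sample noncentral t calculation with d = 1.184 gives 70.7%, 87.9%, 95.4% and 98.4% at 10, 15, 20 and 25 per group. This matches the table exactly, so the stated power is correct at unadjusted alpha 0.05.

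**Error rate, independent tests, every organism null.** With Bonferroni over the reported set, the threshold is c = 0.05/(11 + k). The additions are the smallest p-values among the unlisted targets. If any unlisted p-value is below c, the smallest one is, and it is in the reported set. A false finding therefore occurs exactly when any of the M p-values is below c:

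FWER = 1 − (1 − 0.05/(11 + k))^M

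- M = 96, k = 5: 1 − (1 − 0.05/16)^96 = 0.26
- M = 96, k = 10: 1 − (1 − 0.05/21)^96 = 0.20
- M = 96, k = 20: 1 − (1 − 0.05/31)^96 = 0.14
- M = 30, k = 5: 1 − (1 − 0.05/16)^30 = 0.09
- M = 30, k = 10: 1 − (1 − 0.05/21)^30 = 0.07
- M = 200, k = 10: 1 − (1 − 0.05/21)^200 = 0.38

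**Correlated tests.** Abundances are correlated, and genus and species measures are nested. Simulation with pairwise correlation 0.5 (at least 20,000 runs per case) gives 0.12, 0.10 and 0.07 for M = 96 and k = 5, 10 and 20. For M = 30 and k = 10 it gives 0.046, which is no inflation.

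**A different correction over the same set.** Benjamini-Hochberg over the reported set does not cure this. By simulation, for 96 independent targets, the chance of any false finding is 0.30 with 5 additions and 0.23 with 10.

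**When the family is fixed.** Bonferroni over ten fixed taxa gives 1 − (1 − 0.005)^10 = 0.049. Over all 96 targets it gives 1 − (1 − 0.05/96)^96 = 0.049. Either holds the rate.

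**Power at the corrected alpha.** Effect sizes for the other taxa were solved from the 10-per-group column; they reproduce the remaining columns to within 0.1 point. At 25 per group and alpha 0.05/10 = 0.005:

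| Taxon | Stated | At 0.005 |
|---|---|---|
| *Odoribacter* (lowest of the eight at 91–100%) | 91.2% | 67% |
| *Sutterella* | 91.5% | 67–68% |
| *Alistipes onderdonkii* | 98.4% | 89% |
| *Prevotella* spp. (highest) | 100.0% | 100% |
| *Lachnoclostridium* | 66.4% | 32% |
| *Streptococcus salivarius* | 61.2% | 27% |

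**The case against.** The strongest reply is that the plan states only a possibility. It says organisms may be added, not that they will be chosen by observed shift, and it promises a correction without restricting it to the reported organisms. A reader might infer that the trial will select on results and that 0.05 will not hold. The documents do not support that. Control is lost only if additions come from the outcome data and the correction is confined to the chosen set, and the plan commits to neither. This stands, and it is why the point is conditional.

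A reader might also take 96 as this trial's assay size, from "Fecal microbiome analysis of the subjects using the BIAFAC 96 well qPCR array". That sentence, in the background on PASC, concerns two post-COVID subjects whose data Statistical Considerations places under another IRB number. Wells also need not equal organisms. The 96 is an assumption, as are 30 and 200.

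A reader might further cite "Data will be reviewed on a weekly basis by the PIs and the research team" as evidence of repeated looks at organism shifts. It sits in the Data Safety and Monitoring Plan and does not mention microbiome results by group. The laboratory procedures describe batched, coded specimens. It is not evidence of such looks.

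Two further points stand. The aims are framed as characterisation, in a study the plan calls mechanistic. And the sentence permitting additions names only mTBI against household controls, although no closed list exists for the Arm 2 or PASC comparisons either. None of this supplies the missing family, method or lock date on an outcome that the plan labels primary and tests at 0.05.

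**Conclusion.** The point holds in conditional form. The plan gives explicit permission to enlarge the primary organism comparison and states no rule that would keep the error rate at 0.05 when it is used. If additions follow observed group differences and the correction counts only reported organisms, the chance of at least one false finding runs from about 5%, in a small and strongly correlated pool, to 38% with 200 independent targets and ten additions. These figures assume that every organism is null and that the most-shifted organisms are the ones added. The size cannot be narrowed without the number of targets assayed and the selection rule. The stated power figures are arithmetically right but do not reflect the promised correction.

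**What to change.** Amend Statistical Considerations before any group-labelled microbiome data are reviewed:

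- Lock a confirmatory organism list for the patient-versus-control comparisons. One candidate is the ten listed taxa, with 16S kept as a load check, plus any organism the team already has reason to test, such as *P. copri*, whose absence the background reports.
- Name the correction and apply it over exactly that list.
- Do not test *Prevotella* spp. as an outcome in Aim 1b, where its presence defines the groups and the test would be circular.
- Report every other organism as exploratory, with false-discovery-rate q-values whose denominator is all targets assayed on that platform, whether or not they are shown.

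Correcting over every target assayed would also hold the error rate, but at a higher cost in power. For the lowest of the eight organisms stated at 91–100%, power at 25 per group falls to about 38% with Bonferroni over an assumed 96, against about 67% over ten.

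The text change is short, but there are two costs. An organism not on the list can be reported only as exploratory. The power statement must also be redone at the corrected alpha: with Bonferroni over ten at 25 per group, the eight organisms have about 67–100%, and the two stated at 66% and 61% have about 32% and 27%. Adding organisms to the list lowers these further.

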Title: Brain and Gut Plasticity in mild TBI or post-acute COVID Syndrome Following Growth Hormone Therapy

Principal Investigator: [name]., Internal Medicine, UTMB

Co-I: [name]., Internal Medicine, UTMB

Co-I: [name]., Pediatrics, UTMB

Co-I: E. [name]., Internal Medicine, UTMB

Institution: The University of Texas Medical Branch at Galveston

Sponsors: The Moody Endowment

Sealy & Smith Foundation

Specific Aims

Increasing evidence suggests the gastrointestinal (GI) microbiome is altered in patients with history of mild traumatic brain injury (mTBI). In this project, we propose to characterize the GI microbiome in patients with a history of mTBI or post-acute COVID syndrome complex (PASC) in comparison to healthy controls. Furthermore, we propose to investigate the potential effects of recombinant Human Growth Hormone (rhGH, given as somatropin, a polypeptide hormone (GENOTROPIN)) on the GI microbiome, fatigue, cognition, brain activation, and brain morphology in individuals with a history of mTBI or PASC.

Specific Aim 1a. To characterize the GI microbiome in patients with a history of mTBI compared to controls. - mTBI Baseline vs. Control Baseline - Fecal samples for determination of the GI microbiome will be collected monthly from mTBI subjects and healthy controls over 6 months to examine the diversity of the microbiome within and between groups. **Outcomes:** Genus, species, q-PCR for selected marker organisms.

Specific Aim 1b. To characterize the GI microbiome in patients with a history of mTBI based on presence of *Prevotella spp.* - mTBI *Prevotella spp.* positive Baseline vs. mTBI *Prevotella spp.* negative Baseline - Fecal samples for determination of the GI microbiome will be collected monthly from mTBI subjects over 6 months to examine the diversity of the microbiome within and between groups. **Outcomes:** Genus, species, q-PCR for selected marker organisms

Specific Aim 2. To characterize the GI microbiome in patients with a history of post- COVID-19 syndrome (PASC) compared to arm 2 controls. - PASC Baseline vs. Control Baseline - Fecal samples for determination of the GI microbiome will be collected monthly from PASC subjects over 6 months to examine the diversity of the microbiome within and between groups. **Outcomes:** Genus, species, q-PCR for selected marker organisms.

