5. Any history of a recently (12 months) diagnosed cancer other than a skin cancer (excluding melanoma).
6. Current alcohol or drug abuse.
7. Premorbid history of psychiatric disorder.
8. Premorbid history of head trauma.
9. Pregnancy or become pregnant during the trial.
10. Subjects who are deficient in cortisol or thyroid at screening will be excluded until hormone abnormalities have been corrected.
11. Subjects with chronic pain who are being managed with narcotics will be excluded as the effects of central nervous system depressants may interfere with study test results.
12. Subjects with a history of inflammatory bowel disease, Celiac disease or active diverticular disease.
13. Other medical condition or medication administration deemed exclusionary by the study investigators.

Healthy Control Inclusion criteria

1. Ages 18-70 years.
2. Participant is willing and able to give informed consent for participation in the study.

Healthy Control Exclusion criteria

1. Significant heart, liver, kidney, blood or respiratory disease.
2. Uncontrolled Diabetes mellitus.
3. Any history of a recently (12 months) diagnosed cancer other than a skin cancer (excluding melanoma).
4. Current alcohol or drug abuse.
5. Premorbid history of psychiatric disorder.
6. Premorbid history of head trauma.
7. Pregnancy or become pregnant during the trial.

8. Subjects who are deficient in thyroid at screening will be excluded until thyroid hormone is replaced.
9. Subjects with a history of inflammatory bowel disease, Celiac disease or active diverticular disease.
10. Other medical condition or medication administration deemed exclusionary by the study investigators.

ARM 3 (PASC):

Inclusion criteria

1. Male or female with a history of COVID with diagnosis confirmed by PCR test.
2. Minimum of 6 months since diagnosis of COVID by PCR test.
3. Ages 18 to 70 years.
4. Score of 3 or higher on any question 1-3 of the Brief Fatigue Inventory (BFI) questionnaire.
5. Participant is willing and able to give informed consent for participation in the study.

Exclusion criteria

1. Current COVID infection.
2. Unable to walk unassisted.
3. Significant heart, liver, kidney, blood or respiratory disease as determined by Principal Investigator.
4. Uncontrolled diabetes mellitus.
5. Any history of a recently (12 months) diagnosed cancer other than a skin cancer (excluding melanoma).
6. Current alcohol or drug abuse.
7. History of psychosis.
8. Pregnancy or become pregnant during the trial.

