9. Subjects who are being managed with narcotics will be excluded as the effects of central nervous system depressants may interfere with study test results.
10. Other medical condition or medication administration deemed exclusionary by the study investigators.

Sources of materials. We will obtain blood, urine, fecal, questionnaire and imaging data from the mTBI and PASC subjects and blood, urine, fecal and questionnaire data from the control subjects. All data/samples will be collected solely for the purpose of experimentation, except for the safety check visit for mTBI and PASC patients at month 1. The blood will be used for screening and to measure metabolites, amino acids and hormones. Fecal samples will be used for determination of the GI microbiome. Questionnaire data will be used to assess GI health and quality of life.

Recruitment Methods and Consenting Process (Arm 1)

- a. Potential mTBI subjects may be patients of the investigators.
- b. mTBI subjects will be recruited through ads and flyers around the community as well as in [name] Medicine Endocrinology clinic. The study will also be listed on the UTMB clinical research website, researchmatch.org and clinicaltrials.gov. Potential subjects may be

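### Arm 3 (PASC) omits the gut-disease and head-trauma exclusions that the Arm 2 controls carry, leaving an avoidable possible confounder of unknown size in the Aim 2 microbiome comparison

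*Combined protocol and SAP*

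**What the plan says.** Specific Aim 2 sets out to characterise the gut microbiome in "patients with a history of post- COVID-19 syndrome (PASC) compared to arm 2 controls", baseline against baseline. Statistical Considerations (Aim 2) gives the size as "at least 25 PASC subjects to compare to 25 normal controls already included in this protocol".

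The eligibility lists are under Protection of Human Subjects:

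- **Arm 2 healthy controls.** Item 9 excludes "Subjects with a history of inflammatory bowel disease, Celiac disease or active diverticular disease". Item 6 is "Premorbid history of head trauma".
- **Arm 1 mTBI, Arm 1 household controls, Arm 2 mTBI.** Each carries the same gut-disease item (items 12, 9 and 12) and the same head-trauma item (items 8, 6 and 8).
- **Arm 3 (PASC).** There are ten exclusions. None names a gut disease or head trauma, the inclusion criteria do not restrict either, and no reason for the difference is stated.

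Arm 3 item 10 is the general clause, "Other medical condition or medication administration deemed exclusionary by the study investigators"; the control list has the same clause as its own item 10. The statistical section says that age and other covariates will enter the model where possible, to deal with random differences between groups. It names neither condition.

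**The concern.** The Aim 2 outcome is the gut microbiome. The gut-disease exclusion sits in all four Arm 1 and Arm 2 lists, so the sponsor evidently thought these diseases could disturb the measurement. The Specific Aims also start from the premise that the microbiome is altered after mild TBI, so on the protocol's own reasoning an old head injury is related to the outcome.

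If both conditions are barred from the controls and allowed in the PASC group, a difference in an organism's abundance could partly reflect gut disease or head injury and be read as an effect of PASC. For head injury a route is at least conceivable. Arm 3 selects on fatigue and a low growth-hormone response, which is the screen used for the mTBI groups. It also recruits in part through an endocrinology clinic and from the investigator's previous research subjects. The documents do not say how often this would bring in someone with an old head injury.

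**Working it through.** **1. The two lists side by side (Arm 2 healthy controls against Arm 3).**

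- Listed gut disease: excluded in controls (item 9), not named in Arm 3.
- Head trauma: excluded in controls (item 6), not named in Arm 3.
- Psychiatric history: any premorbid disorder in controls (item 5), psychosis only in Arm 3 (item 7).
- Thyroid deficiency until replaced: controls (item 8), not in Arm 3.
- Narcotics: not in controls; Arm 3 item 9 reads "Subjects who are being managed with narcotics will be excluded".
- Current COVID infection and inability to walk unassisted: Arm 3 (items 1 and 2), not in controls.

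The first two bear most directly on a microbiome outcome, given what the protocol itself says and does.

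**2. The plan's own power figure.** The statistical section uses a two-group, two-sided t-test at 0.05 and, for *Alistipes onderdonkii*, states "Effect size in this case was 1.184". Power comes from the noncentral t distribution with noncentrality d × √(n₁n₂/(n₁+n₂)). At 25 per group this is 1.184 × √12.5 = 4.19 on 48 df, giving 98.4%. At 10, 15 and 20 per group it gives 70.7%, 87.9% and 95.4%. All four match the table. Solving the same formula for other rows gives d = 1.856 for *Prevotella* spp (97.5% at 10 per group) and d = 0.956 for *Odoribacter* (91.2% at 25 per group).

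**3. Illustrative bias.** The documents give neither the prevalence nor the effect of these conditions in PASC, so both are assumed. Suppose PASC has no true effect, k of the 25 PASC subjects are affected, and each is shifted by d = 1.184 to 1.856 SD. The spurious mean difference is (k/25) × d:

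- k = 2: 0.09 to 0.15 SD
- k = 3: 0.14 to 0.22 SD
- k = 5: 0.24 to 0.37 SD

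Simulated false-positive rates (pooled t-test, 25 against 25, 600,000 runs per cell):

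| Affected of 25 | Full shift, α = 0.05 | Half shift, α = 0.05 | Full shift, α = 0.05/11 |
|---|---|---|---|
| 1 | 5.0% | 5.0% | – |
| 2 | 5.6–6.3% | 5.2–5.4% | 0.5–0.6% |
| 3 | 6.8–8.8% | 5.4–6.1% | 0.7–1.0% |
| 5 | 10.8–17.6% | 6.6–8.8% | 1.5–2.6% |

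The last column assumes Bonferroni over the 11 listed targets (0.05/11 = 0.45%). The plan promises a multiplicity correction but names no method.

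**4. Cost of a sensitivity analysis.** For *Odoribacter*, the weakest of the eight organisms the plan puts at 91–100% power, leaving out 3 PASC subjects gives noncentrality 0.956 × √(22×25/47) = 3.27 and power 89.3%. Leaving out 5 gives 0.956 × √(20×25/45) = 3.19 and 87.6%. The starting value is 91.2%. For *Alistipes* the figures are 98.4%, 97.7% and 97.1%. All are at uncorrected 0.05.

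**The case against.** The strongest reply has four parts.

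- **Cover already exists.** Arm 3 subjects have a medical history and physical, item 10 lets investigators exclude case by case, the pre-screening sheet may already ask, and covariates may be added. This stands in part: the imbalance is possible, not certain. But item 10 is discretionary and sits beside the named exclusions in the control list. A clinical history from the past 3 months may replace the study history, with nothing requiring it to cover either condition. The covariate wording names neither condition and is aimed at random differences. Monthly gut-symptom scores do not diagnose these diseases.
- **The size is assumed.** This stands. The shifts are TBI-against-control differences and may not apply to gut disease or an incidental old head injury. With 1 or 2 affected subjects the effect is negligible, the upper figure needs 5 of 25 affected, and a multiplicity correction lowers the absolute rates.
- **Head trauma is not a like-for-like exclusion across groups.** A reader might infer that every other group is free of head injury. That is not so: mTBI subjects have one by definition, and for them the item most naturally means trauma before the index injury. The relevant comparator is the control list alone.
- **The lists differ in both directions.** This stands. A reader might also want narcotic-managed controls removed to restore symmetry. The protocol's stated reason for that item is interference with study test results, and nothing in the documents ties narcotics to the microbiome, so there is no documentary basis for that step.

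**Conclusion.** The point holds as a minor design weakness confined to Aim 2. The omission is plain in the text, it concerns conditions that the protocol itself treats as relevant to the outcome, and no reason is given. Its size cannot be derived. Under the assumed full shifts and an uncorrected test it is negligible at 1–2 affected subjects of 25 and reaches 7–9% at 3 and 11–18% at 5.

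A reader might infer that the Aim 2 comparison is already biased, or that Arm 3 contains such patients. The documents show only that the criteria allow it. A reader might also infer that aligning these two items would make any remaining difference attributable to PASC. It would not: the comparison is not randomised, PASC subjects are selected on fatigue and growth-hormone response while controls are not, and the psychiatric, thyroid, narcotic, COVID and walking items would still differ. The before-and-after comparisons, in which each subject's baseline is the control, are not shown to be affected.

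**What to change.** Add the gut-disease and head-trauma exclusions to the Arm 3 list. Ask about both explicitly at Arm 3 screening, including when a recent clinical history stands in for the study history. If the pre-screening sheet already asks, this only brings the protocol into line with practice.

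For subjects already enrolled, or if the sponsor keeps the Arm 3 list and states why, record both conditions and prespecify one Aim 2 sensitivity analysis that leaves out the affected PASC subjects and keeps all controls.

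The cost is two eligibility lines, two screening questions and one extra analysis. A few PASC patients may become ineligible, or the sensitivity analysis loses the small amount of power shown in step 4 of the working.

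### PASC patients are excluded only for psychosis but their Aim 2 controls for any premorbid psychiatric disorder, so non-psychotic psychiatric history can sit on the PASC side only and cannot be adjusted away

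*Combined protocol and SAP*

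**What the plan says.** Specific Aim 2 reads: "To characterize the GI microbiome in patients with a history of post- COVID-19 syndrome (PASC) compared to arm 2 controls". Statistical Considerations, Aim 2, plans "enrollment of at least 25 PASC subjects to compare to 25 normal controls already included in this protocol" and says of the TBI power figures: "we expect that the Power calculations explained in this section (above) will also apply to PASC".

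The eligibility lists under Protection of Human Subjects set the two sides of that comparison:

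- Arm 3 (PASC), exclusion 7: "History of psychosis".
- Arm 2 healthy controls, exclusion 5: "Premorbid history of psychiatric disorder".

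The broader item also applies to the Arm 1 mTBI patients, the household controls and the Arm 2 mTBI patients. Arm 3 is the only group of the five with the narrower one, and no reason is given. Both lists end with the same discretionary item: "Other medical condition or medication administration deemed exclusionary by the study investigators".

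The analysis text in Statistical Considerations names age and unspecified other covariates, and promises a multiple-testing correction without naming the method.

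**The concern.** Aim 2 exists to attribute microbiome differences to PASC. A person treated for depression for years before COVID can enter as a patient, while someone with the same history cannot enter as a control. A baseline difference in an organism could then partly reflect earlier psychiatric illness or its drugs. The protocol's own rationale is a gut-brain axis, and it excluded this history in every other group, so it evidently regarded the factor as relevant.

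Modelling does not repair this. To adjust for a factor, some subjects on each side must have it. Here the controls have none by design, so the model would have to extrapolate. A multiplicity correction limits chance findings across organisms and does not remove a systematic shift between groups.

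**Working it through.** **1. Reproduce the plan's figure.** Inputs from Statistical Considerations: two-group t-test, two-sided alpha 0.05, effect size 1.184 for *Alistipes onderdonkii*. With n per group, df = 2n − 2 and noncentrality = d × √(n/2), power from the noncentral t distribution is:

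| n per group | Plan | Recomputed |
|---|---|---|
| 10 | 70.7% | 70.7% |
| 15 | 87.9% | 87.9% |
| 20 | 95.4% | 95.4% |
| 25 | 98.4% | 98.4% |

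The plan's arithmetic is sound. The issue is comparability of the groups, not sample size.

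**2. Spurious difference.** Let a share q of PASC patients have a pre-COVID non-psychotic psychiatric disorder, and let their abundance of an organism be shifted by δ SD. With no such controls and no true PASC effect, the expected group difference is q × δ. Neither q nor δ is in the documents; the values below are assumptions.

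- q = 20%, δ = 0.5: 0.20 × 0.5 = 0.1 SD
- q = 40%, δ = 0.5, or q = 20%, δ = 1: 0.2 SD
- q = 30%, δ = 1: 0.3 SD

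**3. False-positive rate at 25 per group.** Noncentrality = qδ × √(25/2) = qδ × 3.536, df = 48. The critical value is 2.011 at alpha 0.05 and 2.977 at 0.05/11 = 0.45%. Bonferroni over the 11 targets in the power table is an assumption, since the plan names no method.

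| Spurious shift | Noncentrality | Unadjusted (nominal 5%) | Bonferroni, 11 targets (nominal 0.45%) |
|---|---|---|---|
| 0.1 SD | 0.354 | 6.4% | 0.7% |
| 0.2 SD | 0.707 | 10.7% | 1.6% |
| 0.3 SD | 1.061 | 18.0% | 3.4% |

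Correction makes the absolute rates small, but the relative inflation is larger: 3.4/0.45 is about 7.6-fold, against 18.0/5 = 3.6-fold unadjusted.

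Simulation (40,000 trials per setting), which lets the mixture widen the PASC variance, gave 6.4% for q = 20%, δ = 0.5 and 10.5% for q = 40%, δ = 0.5. With the same criterion on both sides it gave 4.9%.

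**4. Scale.** The plan's 93.9% power for *Ruminococcus bicirculans* at 25 per group back-solves to d = 1.01. The δ = 1 cases thus assume a psychiatric effect as large as the whole TBI-control difference for that organism, and belong at the upper end. The 95% interval half-width at 25 against 25 is 2.011 × √(1/25 + 1/25) = 0.57 SD, so the assumed bias is at most about half of it.

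**The case against.** The strongest reply is that the consequence is assumed. Nothing in the documents says how common such history is in PASC or that it moves any listed organism, and the mildest case barely leaves 5%. That stands: the asymmetry is a fact, but its size is unknown. It also stands that the unadjusted rates are not those of the planned analysis, which includes a multiplicity correction.

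A broader PASC population is defensible. Anxiety heads the protocol's list of common PASC symptoms, separating onset before and after COVID by history is imprecise, and premorbid has no index illness in a healthy control. This is a reason to state the choice. It does not make the groups comparable. The discretionary exclusion could remove some PASC patients, but it names no psychiatric condition and is identical in the control list, so it does not restore symmetry.

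Stronger readings a reader might infer are not supported:

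- *Psychotropic drugs occur only in PASC.* Neither list names them; a control could take one for another indication. Only treatment of a prior psychiatric disorder is confined to one side.
- *The imbalance is unmeasurable because controls do not complete the BDI-II.* That scale rates symptom severity, not history before COVID, and a medical history is taken at screening in both groups. The obstacle to adjustment is lack of overlap.
- *Aim 3 is compromised in the same way.* It relates within-person changes from baseline to month 6. Fixed history matters there only if it modifies the response, which nothing in the documents shows.
- *Psychiatric fatigue alone could bring a patient in.* The Arm 3 design text also requires a glucagon-stimulated GH peak below 10 ng/mL.

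Psychiatric history is also one of several differences. Head trauma, thyroid deficiency, and inflammatory bowel, celiac and active diverticular disease are excluded in Arm 2 controls but not listed for Arm 3. This widens the need to align the lists and does not excuse this item.

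**Conclusion.** The point holds as a comparability weakness in Aim 2. Non-psychotic psychiatric history, and largely its treatment, can be present in PASC patients and is excluded in their controls; no reason is given, and covariates cannot correct it. The bias cannot be sized from the documents. The error rates above rest on assumed shifts of 0.1 to 0.3 SD, no true PASC effect and a two-sample t-test as in the power section, and the Bonferroni column further assumes that method over the 11 listed targets.

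A reader might conclude that the Aim 2 comparison is invalid or that its error rate is known to be inflated. The documents support neither: if prevalence or shift is small, the effect is negligible. They support only that a positive result would be open to this alternative explanation, with nothing planned to examine it.

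**What to change.** Reconcile the Arm 3 and Arm 2 control exclusion lists on psychiatric history, or state why they differ. Which rule is right is for the investigators.

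At minimum, and without changing eligibility:

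1. Record pre-COVID psychiatric history and current psychotropic treatment at the existing screening history and physical. Arm 3 may substitute a clinical history up to three months old, so put the item on the study form.
2. Prespecify that the Aim 2 comparison is reported for all PASC patients and again with those patients left out.
3. Judge consistency by effect estimates and confidence intervals, not by requiring significance in both analyses. With 15 PASC patients left (q = 40%) against 25 controls, power falls from 91% to 81% for *Odoribacter* and from 66% to 54% for *Lachnoclostridium*. The interval half-width grows from 0.57 to 2.024 × √(1/15 + 1/25) = 0.66 SD. Loss of significance alone would then say little.

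The cost is one history item and one extra analysis, with a smaller and less precise sensitivity set. No visit is added and no recruit is lost. Narrowing Arm 3 eligibility instead would reduce the pool of eligible PASC patients.
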